### **Outcomes**

**Aim 1.** Feasibility is the degree to which the VR treatment can be successfully integrated within the flow of usual care [15]. Feasibility will be measured with a six item survey (**Appendix 5**), based on the Consolidated Implementation Framework [44], that will be administered to 10 clinical staff using REDCap®. Tolerability refers to the prevalence of patient-reported physical (e.g., vertigo, nausea = "cybersickness") and emotional (e.g., fear and anxiety) adverse effects of the VR treatment, along with any discomfort or inconvenience related to the VR equipment (e.g., ill-fitting headset, facial discomfort, inability to explore the three-dimensional environment fully due to limited mobility, etc.) [2, 39]. Tolerability data (complaints and adverse events frequencies) will be extracted from detailed meeting minutes where such events are reported and discussed.

**Aim 2.** See **Table 2**.

**Table 2** Aim 2 Outcome variables and covariates

Variable	Definition	Source
Outcomes		
Hand dexterity Appendix 6	Action Research Arm Test (MCID*: chronic=5.7, acute=12) [45, 46] Primary	Clinical assessment and Self-report
Neurologic recovery Appendix 7	Fugl-Meyer Assessment of Motor Recovery after Stroke-UE MCID*=4-7 [47] Primary	
Pain Appendices 8 and 9	Pain Outcomes Questionnaire-VA, Initial, item 12 and Discharge, item 2 (Pain Numeric Rating Scale) (ES*= 0.85, medium effect, SEM*=0.79) [48] Secondary	
Demographic and Clinical		
Age	Age on date of baseline data collection	CPRS
Sex	Male, female	
Race/ethnicity	Caucasian, African American, Hispanic, other	
Time since index stroke	In days: index event - baseline data collection	
Type stroke	Ischemic =0, hemorrhagic =1	

\* MCID=Minimal Clinically Important Difference, ES=Effect Size, SEM=Standard Error of Measurement, CPRS=Computerized Patient Record System

**Analyses.** With the proposed pilot study design, the overall analytic goals are to: (1) determine the feasibility and tolerability of using a therapeutic VR platform in an inpatient comprehensive stroke rehabilitation program and to (2) estimate, with reasonable precision, the effect sizes of **upper extremity neurologic recovery, hand dexterity, and pain reduction outcomes**.

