**Aim 2.** For **RQ 2.1**, the primary outcomes will consist of pre- to post-intervention changes on two physical measures of stroke recovery: the Action Research Arm Test (ARAT) [45] (Appendix 6) and the Fugl-Meyer Assessment of Motor Recovery after Stroke-Upper Extremity [47] (Appendix 7). Both of these measures are scored on a continuous scale, as is the outcome of pain, as listed in **Table 2**. Therefore, the initial step will be to examine distributions of each outcome measure, including distribution of change scores from pre- to post-intervention. To estimate effect sizes over 4 weeks with the use of the VR platform, standardized effect sizes and 95% confidence intervals will be calculated using the within-group pre-test/post-test design described by Morris and DeShon (2002) [50] and Kadel and Kip (2012) [51]. Recognizing the pilot study design, yet concern over potential type I error due to multiple outcomes evaluated, the confidence intervals for the two co-equal primary outcomes will be evaluated with a type I error rate of 0.025 (i.e. to determine if the confidence interval for the outcome difference scores includes the null effect size value of 0); secondary outcome will be evaluated with a type I error rate of 0.01. The above confidence interval approach parallels use of the paired *t*-test to determine statistical significance. For **RQ 2.1**, since the effect sizes to be calculated are standardized measures, corresponding results across these outcomes will be directly comparable. However, these metrics do not necessarily translate to meaningful clinical differences (improvements). Therefore, for those outcome measures with published metrics for minimal clinically important difference (MCID) [52], results of the VR platform will be compared across outcomes. As listed in **Table 2**, the measures of dexterity and neurologic recovery have published references for MCID, whereas we are unaware of a published MCID for the Pain Outcomes Questionnaire VA (POQ-VA). Therefore, for the POQ-VA, we will first determine the change (pre versus post scores) in

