standard deviation units (from the baseline value) that denotes MCID for the measures of dexterity and neurologic recovery. We will then average these two calculations of standard deviation units to estimate the magnitude of change in pre-to-post scores on the POQ that may approximate MCID on this measure. Thus, in addition to comparison of standardized effect sizes across the three outcomes measures, all three measures will be compared in terms of proportion of subjects who experience MCID.

**Potential Limitations and Strategies.** As this pilot study will employ a within-subject design to evaluate magnitude of stroke rehabilitation over 3 weeks with the use of VR technology, there will be no control condition to judge rehabilitation results to that which might be expected from time alone and natural history of stroke recovery. Therefore, as described for **RQ 2.1**, we will place a premium on evaluating rehabilitation results using MCID, which are highly relevant to patients and generally would not be expected to be achieved simply from time alone (4 weeks).

**Project Management Plan. Personnel.** **[name]** will lead the administrative and scientific aspects of the project and will be responsible for recruitment and collection of medical data. **[name]** will oversee data management, analysis, and assist with interpretation of data. **Project Manager [name]**, an Occupational Therapist (OT), will obtain informed consent, perform pre and post data collection, **instruct study subjects in use of VR technology**, and enter data into the study dataset. **[name] and PI [name]** will perform initial technical assessment, instruct clinicians in use of VR technology, and update APPs weekly to meet individual patient needs. **[name]** will serve as a Research Mentor and can provide OT expertise. **[name]** will serve as our Program Partner from the Physical Medicine and Rehabilitation Office.

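### The pain MCID cutoff is built from two motor MCIDs and has no pain anchor, so the pain responder proportion should not be compared with the motor ones

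*Combined protocol and SAP*

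**What the plan says.** The rule is in the combined protocol and SAP, under Outcomes, in the Aim 2 analysis paragraph. After describing standardized effect sizes, the plan adds a clinical yardstick: "for those outcome measures with published metrics for minimal clinically important difference (MCID) [52], results of the VR platform will be compared across outcomes". Table 2 gives published MCIDs for the ARAT (5.7 chronic, 12 acute) and the Fugl-Meyer upper-extremity score (4 to 7). The authors say they know of none for the POQ-VA.

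They therefore set out a workaround for pain. They will first find the change in "standard deviation units (from the baseline value) that denotes MCID for the measures of dexterity and neurologic recovery". Then: "We will then average these two calculations of standard deviation units to estimate the magnitude of change in pre-to-post scores on the POQ". The plan says only that this magnitude might come close to an MCID. The next sentence states that "all three measures will be compared in terms of proportion of subjects who experience MCID".

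Under Potential Limitations and Strategies, the plan acknowledges that there is no control condition and says that for this reason "we will place a premium on evaluating rehabilitation results using MCID". It argues that changes of MCID size matter to patients and would not usually come from time alone.

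**The concern.** An MCID is meant to mark a change that matters on the scale in question. The pain cutoff here takes its multiplier from two arm-function scales. No patient judgement of worthwhile pain relief enters it, and neither do the pain metrics in Table 2 ("ES*= 0.85, medium effect, SEM*=0.79"). The only pain quantity is the baseline SD of the pain score, which converts the multiplier into points.

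The result has an odd property. Each motor MCID is a fixed number divided by the spread of arm scores. A sample with more mixed arm impairment therefore gets an easier pain bar, even if nobody's pain differs.

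At stake is how the pain proportion is read. The plan leans on MCID because it has no control group. Its argument that such changes would seldom arise from time alone is made for MCIDs. Nothing in the documents extends it to a cutoff borrowed from other constructs. Set beside two proportions based on published MCIDs and under the same label, the pain figure would look equally well supported when the larger trial is planned.

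**Working it through.** The plan gives no numeric pain cutoff, so there is no figure to reproduce. The rule can be written out and evaluated.

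**Inputs**
- ARAT MCID 12: Table 2's acute value, used because patients are admitted after acute stroke.
- Fugl-Meyer MCID 5.5: the midpoint of Table 2's 4 to 7, chosen here for illustration.
- Number of patients, 10: Population.
- Baseline SDs: not given in the documents, and their source is not named. All SDs below are assumptions.

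**Formula**

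multiplier = ½ × (MCID_ARAT / SD_ARAT + MCID_FMA / SD_FMA)

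pain cutoff = SD_pain × multiplier

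Every term in the multiplier is a motor quantity. This holds whatever the source of the SDs.

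**Dependence on arm-score spread.** With both motor SDs equal to s and a pain SD of 2.5, the cutoff is 2.5 × (12 + 5.5) / (2s) = 21.875 / s.

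| Motor SD (assumed) | Multiplier | Pain cutoff, points |
|---|---|---|
| 10 | 0.875 | 2.19 |
| 15 | 0.583 | 1.46 |
| 20 | 0.438 | 1.09 |
| 25 | 0.350 | 0.88 |

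The pain SD is the same in every row. Only the spread of arm scores changes, and the cutoff moves by a factor of 2.5.

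**Other inputs.** At motor SD 20, moving the Fugl-Meyer MCID from 4 to 7 moves the cutoff from 2.5 × 16 / 40 = 1.00 to 2.5 × 19 / 40 = 1.19. With motor SDs of 15 to 25, pain SDs of 2 to 3 and the Fugl-Meyer range 4 to 7, the extremes are 2 × 16 / 50 = 0.64 and 3 × 19 / 30 = 1.90 points.

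**Sampling error if the SDs come from the 10 patients.** This is the natural reading but is not stated. At n = 10, a 95% interval for an SD runs from 0.69 to 1.83 times its estimate. A simulation of repeated samples of 10 took true SDs of 20, 20 and 2.5, normal scores and an ARAT–Fugl-Meyer correlation of 0.9. It spread the 1.09-point case over about 0.55 to 2.16 (95% range). With uniform motor scores the range was 0.57 to 1.89.

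**What a moving cutoff does to the proportion.** Assume whole-point pain scores, a mean improvement of 1.5 and an SD of change of 2. The share improving by at least k points is then 1 − Φ((k − 0.5 − 1.5) / 2): 69% at 1 point, 50% at 2 and 31% at 3. A cutoff of 0.88 requires a 1-point fall, 1.09 or 1.46 requires 2, and 2.19 requires 3. The same pain data could thus give a proportion from 31% to 69% across the table. These figures illustrate the mechanism and do not predict this trial's result.

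**The case against.** The strongest defence is that the plan is open about what it does. It discloses the missing MCID, gives the derivation and says that the result is only an approximation. The comparison follows at once, so an attentive reader has seen the hedge. Distribution-based thresholds are also a recognised fallback. Much of this stands. What it does not answer is that the multiplier is borrowed from other constructs, and that the comparison then uses the plain MCID label for all three measures.

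A reader might infer that the plan contradicts itself, by first limiting the MCID comparison to measures with published values and then including pain. The text does not support this. It introduces the POQ-VA step as a consequence of the missing value, so pain is a declared exception.

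A reader might also infer that omitting pain loses nothing, because RQ 2.2 names only the motor outcomes. That is only half right. The MCID work is described under RQ 2.1, which includes pain, and it is there because standardized effects need not show clinical benefit.

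Two further inferences go too far:
- One could try to say how often the study would end up with a 1-point bar. With the SDs assumed above, that share runs from about 1% (motor SD 10, pain SD 2.5) to 65% (25, 2.5), and to 85% at 25 and 2. No single figure is informative.
- One could say that the 30% pain prevalence cited in the background caps pain responders at 3 of 10. Three is an expected count: 4 or more would have pain with probability 35%. Low baseline pain would also limit response at any cutoff, so it does not bear on the missing anchor.

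**Conclusion.** The point holds and is minor. As written, the rule gives a pain cutoff whose multiplier contains no pain information and which falls as arm scores become more spread out. Comparing the resulting proportion, as MCID, with the ARAT and Fugl-Meyer proportions is not like with like.

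That conclusion follows from the formula and needs no assumption. The size does: 0.88 to 2.19 points rests on assumed motor SDs of 10 to 25, a pain SD of 2.5 and MCIDs of 12 and 5.5. The 0.55 to 2.16 range also assumes that the SDs come from the 10 patients.

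The harm is confined to one secondary comparison in a 10-patient pilot. The standardized pain effect size, its confidence interval and the error rates assigned to the outcomes are unaffected, as are the two motor MCID proportions.

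**What to change.** In the Aim 2 analysis paragraph:

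1. Remove the averaged motor-SD cutoff as a pain MCID.
2. Restrict the comparison of MCID proportions to the ARAT and Fugl-Meyer upper-extremity score, which is the scope of RQ 2.2.
3. For pain, report the standardized effect size and the change in raw points, each with its confidence interval.
4. If a pain responder proportion is kept because RQ 2.1 includes pain, report it separately and label it exploratory and distribution-based. Do not call it MCID or compare it with the motor proportions.

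A replacement cutoff derived from the pain SEM in Table 2 is not needed: it would be another threshold without a pain anchor.

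The cost is a change of analysis wording, with no new data or procedures. The downside is that pain will have no MCID proportion comparable with those of the motor outcomes.

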## Research Design and Methods

**Design.** Our methodological framework is based on the work by Virtual Reality Clinical Outcomes Research Experts (VR-CORE) committee [39]; we will use their VR2 clinical study design: conducting early prospective testing with a focus on feasibility and tolerability (**Aim 1**), and initial efficacy (**Aim 2**). Per VR-CORE guidelines, we will use a single group so that we may optimize recruitment to represent the breadth and depth of our target patients.

**Population.** There are two populations for the proposed project. The first is Veterans ( $N=10$ ) who have been diagnosed with an acute ischemic or hemorrhagic stroke and post-stroke are admitted to JAHVH inpatient rehabilitation. Inclusion criteria are: (1) Age 18-80, (2) Stroke diagnosis verified by brain imaging. Exclusion criteria are: (1) Unable to follow instructions or participate in immersive VR therapy due to significant cognitive impairment, (2) History of seizures. The second population includes the occupational therapists (OT) and the rehabilitation nurses (clinician champions) working in the Comprehensive Interdisciplinary Inpatient Rehabilitation Program, who will provide data on the feasibility of using VR in an inpatient environment (**Research Question (RQ) 1.1**).

**Recruitment.** All patients admitted to the Comprehensive Interdisciplinary Inpatient Rehabilitation Program at JAHVH (a designated Primary Stroke Center) with a diagnosis of acute ischemic or hemorrhagic stroke will be considered for inclusion in the study. A minimum of five beds will be designated for study participants. The Comprehensive Interdisciplinary Inpatient Rehabilitation Program admits 3.5 stroke patients per month, 42 per year. We feel this is a sufficient subject pool from which to enroll the target sample size of **10** patients (**16%** of the patients admitted over the 18-month enrollment period). We have found that the technology is motivating to patients which will help retention.

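### The pain responder cut-off is never checked against the pain item's own SEM and will very probably lie below the change detectable in one patient, so the pain MCID proportion can include re-test error

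*Combined protocol and SAP*

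**What the plan says.** Table 2 (Outcomes, Aim 2) defines the secondary outcome as the POQ-VA pain rating, "Initial, item 12 and Discharge, item 2 (Pain Numeric Rating Scale", and gives its properties as "ES*= 0.85, medium effect, SEM*=0.79". For the two primary outcomes it lists "Action Research Arm Test (MCID*: chronic=5.7, acute=12" and "Fugl-Meyer Assessment of Motor Recovery after Stroke-UE MCID*=4-7".

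The Aim 2 analysis text says the authors know of no published MCID for the POQ-VA and builds one. They first find the change in "standard deviation units (from the baseline value) that denotes MCID for the measures of dexterity and neurologic recovery". Then: "We will then average these two calculations of standard deviation units to estimate the magnitude of change in pre-to-post scores on the POQ". The text hedges the result as something that may approximate an MCID. The cut-off is then applied to individuals, since "all three measures will be compared in terms of proportion of subjects who experience MCID".

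Potential Limitations and Strategies accepts that there is no control condition. It gives the MCID results special weight for that reason, arguing that such changes would not generally be expected from the passage of time alone. The SEM in Table 2 does not appear again in the analysis text.

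**The concern.** A responder proportion classifies each patient on one rating before and one after. If the cut-off is smaller than the re-test variation of that difference, some patients whose pain has not truly changed will pass it by chance. The derived cut-off depends only on the motor MCIDs and the baseline SDs. Nothing in the rule ties it to the precision of the pain item, although the plan holds the figure needed to do so.

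What is at stake is the reading of the pain proportion. The plan relies on MCID results because there is no control arm, and its defence concerns time and natural recovery. Measurement error is a separate source of apparent responders which that defence does not cover. A control group would show the error-driven share; here nothing in the planned MCID report separates it.

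**Working it through.** The documents state no pain cut-off, so there is no figure of the plan's own to reproduce. The written rule is applied directly.

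**Inputs from the documents.** Pain SEM 0.79; ARAT MCID 5.7 (chronic) or 12 (acute); Fugl-Meyer MCID 4 to 7 (all Table 2). The population is patients "diagnosed with an acute ischemic or hemorrhagic stroke" (Research Design and Methods, Population), which points to the ARAT value of 12, although the plan does not say which value enters the average.

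**Assumptions, not in the documents.** Baseline SD 12, 16 or 20 for ARAT and for Fugl-Meyer, and 2, 2.5 or 3 for pain. The SEM is in raw points for a single rating. Ratings are whole numbers where stated.

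**Step 1, error of a change.** SD of the difference of two ratings with no true change = 0.79 x sqrt(2) = 1.12. The 95% minimal detectable change = 1.96 x 1.117 = 2.19 points.

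**Step 2, the cut-off.** Cut-off = 0.5 x (ARAT MCID / ARAT SD + FM MCID / FM SD) x pain SD.

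- Smallest: 0.5 x (5.7/20 + 4/20) x 2 = 0.49.
- Largest: 0.5 x (12/12 + 7/12) x 3 = 2.38.
- Mid-range example: 0.5 x (12/20 + 7/20) x 2.5 = 1.19.

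| ARAT MCID used | Combinations | Range (points) | Median | Below 2.19 | At or below 1 | Below 0.79 |
|---|---|---|---|---|---|---|
| 5.7 or 12 | 108 | 0.49 to 2.38 | 1.09 | 107 | 42 | 17 |
| 12 only | 54 | 0.80 to 2.38 | 1.39 | 53 | 7 | 0 |

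Wider SD ranges (12 to 25 for the motor scales, 1.5 to 3.5 for pain) put the cut-off below 2.19 in 99% of combinations. Allowing for SDs estimated from 10 patients (true motor SDs of 20, pain SD 2 to 3), the probability of falling below 2.19 is 0.91 to 1.00 across the MCID pairs.

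**Step 3, chance of a false responder.** With zero true change and a continuous score, the chance is 1 - Phi(cut-off / 1.117): 33% at 0.5, 19% at 1.0, 9% at 1.5, 4% at 2.0. On whole-number ratings a cut-off up to 1 needs an observed 1-point drop, and one above 1 and up to 2 needs a 2-point drop. Simulated stable patients with true pain between 2 and 8 give about 33% for a drop of at least 1 point, 10% for 2 and 1.5% for 3. With the acute ARAT MCID, 44 of the 54 cut-offs lie above 1 and at or below 2, so about 10% is the typical figure.

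**Step 4, what a stricter threshold misses.** On whole numbers, 2.19 means a 3-point drop. A patient starting at 4 to 6 whose pain truly falls by 2 points is counted 33% of the time under a 3-point rule and 67% under a 2-point rule.

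**The case against.** Two stronger readings are tempting and should be set aside.

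- **A reader might infer that the cut-off nearly always falls within one SEM, 0.79.** It does not: this happens in 17 of 108 combinations and in none of the 54 that use the acute ARAT value. One SEM is also the wrong yardstick for a difference of two ratings.
- **A reader might infer that about 3 in 10 stable patients with pain would be counted.** That needs a scored rule of 1 point, which with the acute value arises in 7 of 54 combinations. Patients who rate 0 at baseline cannot drop at all.

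Other objections carry weight. The Background cites 30% pain prevalence after stroke. If that held here, about 3 of 10 patients would have pain, and error alone would add 3 x 0.10 = 0.3 of a responder under a 2-point rule, or 3 x 0.33 = 1.0 under a 1-point rule, if none had truly changed. Inference on pain rests on a standardized effect and a confidence interval at type I error 0.01, neither of which uses the cut-off. The plan also examines change-score distributions first, so worsening need not go unseen. MCID and minimal detectable change answer different questions. Imposing 2.19 as a floor would miss many true 2-point improvements, and applying it to pain alone would disturb the planned comparison across measures.

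These points rule out a mandatory floor and lower the severity. They do not answer the omission: the plan prints the SEM, classifies individuals, and never compares the two.

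**Conclusion.** The point holds as a minor one. The pain cut-off is not checked against the SEM in Table 2, and it will very probably lie below the 2.19 points needed to tell change from error in one patient. Patients who have pain but no true change would then pass at about 10% under a 2-point rule and about 33% under a 1-point rule. The planned pain MCID proportion therefore cannot, on its own, be read as change beyond error.

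The 2.19 figure needs only Table 2, with the SEM read as raw points for one rating; the table gives neither a unit nor a re-test interval. The position of the cut-off rests on assumed baseline SDs, but its relation to 2.19 hardly moves across the ranges tried. The false-responder rates also assume normal error and, where stated, whole-number ratings. Pain is secondary, N is 10, and the primary outcomes are untouched.

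**What to change.** Keep the derived cut-off and add to the Aim 2 pain rule:

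- Among patients with baseline pain above 0, the responder proportion will also be reported, as a sensitivity result, at the SEM-based threshold of 2.19 points (a 3-point drop on whole-number ratings).
- In the same patients, the number whose pain rose by at least the same amount will be reported beside each proportion.
- Responders who fall between the two thresholds cannot be told from measurement error, and the report will say so.

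The cost is a few sentences and two extra counts, with no new data. The stricter threshold misses many true 2-point improvements, so it should stand beside the planned cut-off and not replace it. The worsening count is only a rough gauge of error, because true recovery would lower it.

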## Specific Aims

Over the last decade, virtual reality (VR) has emerged as a cutting-edge technology in stroke rehabilitation. VR is defined as a type of user-computer interface that implements real-time simulation of an activity or environment allowing user interaction via multiple sensory modalities. VR interventions in a stroke population have been shown to be equivalent to usual care therapies and to enhance motor, cognitive, and psychological recovery when utilized as an adjunct. The proposed feasibility pilot project will address the RR&D goal of maximizing functional recovery by pilot testing an immersive VR intervention designed to increase exercise dosage for the upper limb and decrease pain for inpatient Veterans post stroke without increasing therapist time [1]. **The VR intervention will use a head mounted display, more commonly known as goggles, to which selected APPs can be uploaded. APPs and goggles are commercially available and have been selected based on the following criteria: (1) address the treatment goals of overall upper extremity neurologic recovery, hand dexterity, and pain reduction, (2) utilized while patient lying in bed, (3) provide no stimulation to move legs or reach outside of bed area, (4) simple to use (require no technological expertise), (5) involve graded head, neck, upper extremity movement and distraction to reduce pain, and (6) cognitive burden ranges from minimal to moderate. The VR intervention will be administered bedside for two 30-minute therapy sessions per day for four weeks. Our long-term goal is to provide Veterans with an exercise and pain reduction modality that can serve as an adjunct to scheduled therapy and assist with the clinic to home transition. Our short-term goal is to determine the feasibility of conducting a randomized controlled trial to determine the effectiveness of using VR as an adjunct to usual care therapy to enhance upper extremity neurologic recovery and hand dexterity and to decrease pain.** Our proposal is innovative in four distinct ways. First, we will use immersive 3-dimensional rather than the more typically used 2-dimensional VR. Immersion and the resulting 'presence' within the virtual environment are thought to be the principal mechanisms of positive change [2]. **Second, we will assess pain reduction after stroke using VR APPs, which is not well represented in the literature.** Third, we are using VR as an adjunct therapy - adding additional therapy time with less burden on clinicians than is required in traditional therapy. Finally, VR, when used in patients' rooms, presents an opportunity similar to home-based practice exercises. Our targeted enrollment is 10 clinical staff (Research Question (RQ) 1.1) and 10 inpatient Veterans being treated for stroke (Aim 2).

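### The plan rests its clinical reading on MCID but analyses MCID only as a yes/no count in 10 patients; the error-controlled intervals are read only against 0, and mean change is never set against the MCID

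*Combined protocol and SAP*

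**What the plan says.** The Aim 2 analysis treats ARAT and FMA-UE (primary) and pain (secondary) as continuous. It plans standardized effect sizes with 95% intervals for pre-to-post change. On error control, "the two co-equal primary outcomes will be evaluated with a type I error rate of 0.025" and "secondary outcome will be evaluated with a type I error rate of 0.01". The stated use of the primary intervals is "to determine if the confidence interval for the outcome difference scores includes the null effect size value of 0". The plan likens this to a paired t-test.

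It then cautions that standardized effects need not mean clinical improvement, and brings in MCID for that reason. Table 2 lists 5.7 (chronic) and 12 (acute) for ARAT and 4 to 7 for FMA-UE. Pain has no published MCID, so one is to be approximated from the other two in SD units. The MCID analysis is that, besides the comparison of effect sizes, "all three measures will be compared in terms of proportion of subjects who experience MCID". No interval, benchmark or error rate is given for that proportion.

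Under Potential Limitations and Strategies the plan acknowledges that "there will be no control condition to judge rehabilitation results" and responds that "we will place a premium on evaluating rehabilitation results using MCID".

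**The concern.** The two halves of the analysis do not meet. The intervals with a stated error rate address any change from 0. The result meant to carry the clinical interpretation, and to bear on RQ 2.2 (clinical responsiveness), is a yes/no classification of 10 patients that ignores how far each patient fell from the cut-off. A standardized effect read against 0 cannot be placed directly against an MCID given in scale points, and the plan does not state the step that would link them.

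At stake is the interpretation of a pilot that is to inform a larger trial. A reader could be given a primary change that is statistically different from 0, and a responder count with no interval, without being told whether the mean change is compatible with the MCID.

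**Working it through.** **Inputs.** n = 10, single group (Specific Aims; Design). Error rate 0.025 for each primary outcome, taken as two-sided because the rule is whether an interval includes 0. MCIDs from Table 2. The documents give no SD of change, so 6, 8 and 10 points are assumptions. Ten evaluable patients are assumed.

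**The plan's own figures.** There is no power or precision calculation to reproduce. The recruitment share does reproduce: 3.5 × 18 = 63 admissions and 10/63 = 15.9%, stated as 16%. The two primary error rates sum to 0.025 + 0.025 = 0.05.

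**1. When does the interval exclude 0?** Half-width = t(0.9875; 9 df) × SD/√10 = 2.685 × SD/3.162 = 0.849 SD. The observed mean must exceed this value:

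| Assumed SD | Mean needed (points) | % of ARAT 12 | % of ARAT 5.7 | % of FMA-UE 7 | % of FMA-UE 4 |
|---|---|---|---|---|---|
| 6 | 5.1 | 42 | 89 | 73 | 127 |
| 8 | 6.8 | 57 | 119 | 97 | 170 |
| 10 | 8.5 | 71 | 149 | 121 | 212 |

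The threshold lies below the MCID only if SD < MCID/0.849, that is 14.1 (ARAT 12), 6.7 (ARAT 5.7), 8.2 (FMA-UE 7) or 4.7 (FMA-UE 4). It is half the MCID or less only if SD is below 7.1, 3.4, 4.1 or 2.4 respectively.

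**2. What reading against the MCID adds.** Two illustrations for ARAT:
- SD 6, mean 6: 6 ± 5.1 gives 0.9 to 11.1. This excludes 0 and lies wholly below 12.
- SD 8, mean 7: 7 ± 6.8 gives 0.2 to 13.8. This excludes 0 but is compatible with both 5.7 and 12.

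Under the stated rule both are reported alike. For the lower limit to clear the MCID, the mean must reach MCID + 0.849 SD. At SD 6 that is 17.1 for ARAT 12, 10.8 for ARAT 5.7, and 9.1 to 12.1 for FMA-UE 4 to 7.

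**3. How much the count discards.** Take normal changes with the cut-off c SDs from the mean and p = Φ(c). The efficiency of the count for estimating the proportion, SD unknown, is φ(c)²(1 + c²/2)/[p(1 − p)]:
- c = 0: 0.637 (2/π)
- c = 0.5: 0.654
- c = 1: 0.658
- c = 1.5: 0.572
- c = 2: 0.393

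The loss is therefore 34% to 36% within 1 SD and larger beyond. Simulation at n = 10 (300,000 runs) gave mean squared error ratios, model to count, of 0.70, 0.68 and 0.61 at c = 0, 0.5 and 1, a loss of 30% to 39%.

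**4. Precision of the count.** The exact 95% interval is 19% to 81% for 5 of 10, and 44% to 97% for 8 of 10.

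**5. The same question asked both ways.** Suppose the true mean is 1 SD above the MCID. A sign test needing at least 9 of 10 has two-sided error 2 × 11/1024 = 0.0215 and power 51%. A t-test of the mean against the MCID at the same error rate has power 65%.

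**The case against.** Three readings go further than the documents allow.

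- *A mean change well below the MCID can count as success.* A reader might infer this, but no success or go/no-go rule appears. Aim 2 is to estimate, and the plan itself warns that its effect sizes are not clinical benefit. Only a statement of statistical difference from 0 is possible.
- *A third of the information in the data is lost.* Not across the plan. The sentence containing the responder comparison keeps the continuous effect sizes beside it, and the MCIDs are to be converted to SD units. The loss is confined to the MCID reading.
- *Either primary outcome can be significant at half its MCID.* The table shows otherwise. At larger SDs, a mean that excludes 0 must exceed ARAT 5.7 or the FMA-UE values.

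The count also deserves defending. It is a patient-level summary free of distributional assumptions, and a group mean below the MCID does not mean that nobody benefited: with mean 8.5 and SD 10, about 36% of patients would reach 12 under normality. Replacing the count with a proportion derived from the mean and SD looks attractive, since for 5 of 10 its 95% interval would be 27% to 73% instead of 19% to 81%. But part of that gain reflects the conservatism of the exact interval; a Wilson interval is 24% to 76%. Under assumed skewed changes at cut-off 12 the mean squared error ratio was about 1 (0.96 to 1.19), with coverage of 86% to 91%. Under a responder/non-responder mixture at cut-off 5.7 it was about 1.3, with 13 to 14 points of bias. A normality test at 0.05 flagged these shapes only 20% to 35% of the time.

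All of this stands. It does not supply the missing comparison of mean change with the MCID.

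**Conclusion.** The point holds in limited form. MCID carries the clinical weight but enters only as a yes/no proportion of 10 patients, and the only intervals with a stated error rate are read against 0. About a third of the information bearing on MCID goes unused if change scores are near normal and the cut-off lies near the mean; further out the loss is larger, and under skewed or mixed shapes a normal-model estimate may gain nothing. For ARAT against 12, the interval can exclude 0 at 42% to 71% of the MCID under assumed SDs of 6 to 10, and at less than the MCID for any SD under 14.1. No general statement of that kind can be made for ARAT 5.7 or FMA-UE. This is a reporting gap that is cheap to close, not an invalid analysis.

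**What to change.** In the Aim 2 analysis text, for ARAT and FMA-UE:

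1. Report mean change in scale points with a 97.5% interval, which matches the stated 0.025 error rate (the 95% level now named does not). State where the interval lies relative to each Table 2 MCID value as well as to 0.
2. Keep the observed count out of 10 as the patient-level summary, with an exact interval.
3. Do not substitute a normal-model proportion for the count. If wanted, show it as a sensitivity estimate only.

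The cost is two or three sentences and a few lines of code, with no extra patients, visits or data. Item 1 assumes nothing beyond the planned paired-t-type interval. The downside is presentational: with 10 patients the interval will often be compatible with changes on both sides of the MCID, which may look less favourable than reporting that it excludes 0.
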